11.3.3 Definition of Exploratory Endpoint

Time to initiation of systemic therapy will be calculated as the difference (in days) between the dates of enrollment and initiation of systemic therapy (this difference is 0 when treatment initiation occurs on the date of enrollment). A binary variable indicating if the time to initiation of systemic therapy is less than 0 (i.e., systemic therapy was initiated prior to date of enrollment) will be determined for each subject.

11.4 Analysis Populations

The intent to treat (ITT) population will consist of all randomized subjects. This population will be used to summarize the CONSORT diagram, subject disposition, and baseline subject and disease

characteristics. The evaluable population will consist of all enrolled subjects who meet both of the following criteria:

- Receive at least one dose of standard of care systemic anti-cancer therapy on or after the enrollment date
- Die within six months of enrollment or otherwise are on study for at least 6 months.

The evaluable population will be used for the analyses of all primary, secondary, and exploratory endpoints and interim analyses. Select analyses of time to initiation of systemic therapy will be conducted on the subset of the evaluable population initiating systemic therapy on study only (Section 11.5.6). Additionally, an intervention-compliant population will be defined as all subjects in the evaluable population who meet all of the following criteria:

- Subjects received intervention they were randomized to:
 - Subjects randomized to the ONN arm who have at least one LPNP encounter within 2 weeks from randomization.
 - Subjects randomized to the control arm who do not have any LPNP encounters within 6 months from randomization.

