5.4 Duration of Data Acquisition

Underlying primary data needed to support study endpoints will be acquired by trained study conduct research staff. For each subject, this will be done starting at the day of randomization and then on an every 3-month basis.

The duration of data acquisition will be as follows:

- For ACU, readmissions, adherence to clinical care, and subject satisfaction, the duration of data acquisition will be until the subject meets the criteria for off-intervention (see Section 8.1)
- For survival data, the duration of data acquisition will be until the subject becomes off study (see Section 8.2).

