8. OFF INTERVENTION AND OFF STUDY

8.1 Off Intervention

Subjects will be removed from Intervention Status when at least one of the following criteria are met:

- Subject on either arm who permanently discontinues all active anti-cancer therapy
- Subject on either arm who relocates to a non-LCI institution
- Subject on either arm who relocates to an LCI site without LPNP
- Subjects randomized to the ONN arm withdraws consent to participate in the LPNP

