11.1.2 Enrollment Date

The date that the subject is randomized.

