11.5.4 Primary Analysis

The frequency and proportion of subjects alive at 6 months or better will be calculated for each study arm. Corresponding 95% confidence intervals will be estimated using the Clopper-Pearson method. A

two-sided test for binomial proportions will be carried out, testing the null hypothesis that there is no difference in the OS6 rate between the arms.

Poisson regression analyses will be used to analyze acute care utilization visits. Treatment arm will be included in the model as the primary covariate and an asymptotic test of significance will be carried out to compare acute care utilization between the arms.

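### Both co-primary endpoints are analysed only in a set chosen by post-randomisation events, and no all-randomised effect estimate is planned

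*Combined protocol and SAP*

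**What the plan says.** Section 11.4 defines ITT as everyone randomised, but gives it only descriptive uses. For everything else it says: "The evaluable population will be used for the analyses of all primary, secondary, and exploratory endpoints and interim analyses". A subject is evaluable only if both criteria are met:

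1. "Receive at least one dose of standard of care systemic anti-cancer therapy on or after the enrollment date"
2. "Die within six months of enrollment or otherwise are on study for at least 6 months"

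Section 11.1.2 defines the enrollment date as "The date that the subject is randomized", so both criteria look at events after allocation. The one further set, intervention-compliant, is a subset of the evaluable set.

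Section 11.5.4 tests OS6 between arms ("testing the null hypothesis that there is no difference in the OS6 rate between the arms") and compares ACU by Poisson regression. Neither that section nor Sections 11.5.5 to 11.5.8 adds an all-randomised or sensitivity estimate.

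On data collection, Section 5.4 says "For survival data, the duration of data acquisition will be until the subject becomes off study", whereas for ACU "the duration of data acquisition will be until the subject meets the criteria for off-intervention". Section 8.2 stops all collection once a subject is off study.

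**The concern.** Section 1.2 justifies the trial by saying that the earlier retrospective benefit might reflect biased case selection despite propensity matching. An analysis set chosen on post-randomisation events lets selection back in, and there is no planned result to check it against.

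The two criteria do different damage:

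- **Dose criterion.** A subject who dies without a dose on or after randomisation has a known OS6 outcome and is dropped. No missing-data reason exists for this, because survival is followed until off study whether or not treatment is given.
- **Six-month criterion.** Early deaths stay in, while subjects who leave alive before 6 months are removed. This lowers observed OS6, and more so in the arm with more drop-out. It is partly a genuine missing-data problem, since nothing is collected off study.

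If either exclusion differs by arm in number or prognosis, the arms compared are no longer the arms randomised.

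**Working it through.** **Planning allowance.** Section 11.2 gives 347 enrolled for 300 evaluable: 1 − 300/347 = 47/347 = 13.5%.

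**Inputs for the bias check.** From the documents: control OS6 60%, two-sided alpha 0.025 per co-primary, 347/2 = 173.5 randomised per arm, 6 visits per year. Assumed: no true effect, and all exclusion rates and undosed survival rates below, since the documents give none.

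**Formulas.**
- Dose filter, with undosed share f and undosed OS6 s: OS6 among the dosed = (0.60 − f·s)/(1 − f).
- Drop-out filter, with net 6-month drop-out d: λ = −ln(S)/6, μ = −ln(1 − d)/6; OS6 = P(alive and retained) / [P(alive and retained) + P(died before drop-out)].
- False-positive rate: pooled two-proportion z-test, both tails, n = 173.5 × retained fraction.

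Example: f = 0.10, s = 0.20 gives (0.60 − 0.02)/0.90 = 0.644 in control; f = 0.05 gives (0.60 − 0.01)/0.95 = 0.621 in ONN; the difference is −2.3 points.

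| Scenario (control vs ONN) | OS6 control / ONN | ONN − control, points | False-positive rate |
|---|---|---|---|
| Undosed 10% vs 5%, s = 20% | 0.644 / 0.621 | −2.3 | 0.039 |
| Undosed 10% vs 5%, s = 40% | 0.622 / 0.611 | −1.2 | 0.028 |
| Undosed 15% vs 5%, s = 20% | 0.671 / 0.621 | −5.0 | 0.092 |
| Undosed 15% vs 5%, s = 40% | 0.635 / 0.611 | −2.5 | 0.040 |
| Undosed 15% vs 5%, s = 50% | 0.618 / 0.605 | −1.2 | 0.029 |
| Drop-out 10% vs 5% | 0.586 / 0.593 | +0.7 | 0.026 |
| Drop-out 15% vs 5% | 0.578 / 0.593 | +1.5 | 0.030 |
| Undosed 10% vs 5% and drop-out 5% vs 10%, s = 20% | 0.638 / 0.607 | −3.1 | 0.048 |
| Same, s = 40% | 0.616 / 0.597 | −1.9 | 0.033 |
| Undosed 10% vs 5% and drop-out 10% vs 5%, s = 20% | 0.631 / 0.614 | −1.7 | 0.032 |
| Same, s = 40% | 0.609 / 0.604 | −0.5 | 0.026 |

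These scenarios exclude 20 to 46 subjects, within the allowance of 47. A more lopsided split of all 47 (40 in one arm, 7 in the other, excluded OS6 20% to 40%) gives 5.2 to 10.3 points. An equal split with equal prognosis gives zero.

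**Direction.** With no bias, the false ONN-win rate is 0.0125. Fewer undosed on ONN lowers it: to 0.0037 (10% vs 5%) and 0.0008 (15% vs 5%) at s = 20%. More control drop-out raises it: to 0.024 at 15% vs 5%.

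**ACU.** With true mean 6 in both arms and undosed subjects at k times that rate, the mean among the dosed is 6(1 − f·k)/(1 − f). For k = 0.5, 1, 2 the spurious ONN/control ratio is 0.97, 1.00, 1.07 (10% vs 5%) or 0.94, 1.00, 1.15 (15% vs 5%). The design ratio is 0.80.

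**Power if all 347 were analysed** (pooled z, alpha 0.025):
- The stated 80% at 150 per arm and 60% vs 80% does not reproduce: it is 94.3%. Section 11.5.8 raised n from 107 to 150 per arm to keep 80%, which suggests a smaller working difference. If control stays at 60%, 150 per arm gives 80% power at 16.5 points. This is an inference, because the interim data are not given.
- At 60% vs 80%, 173.5 per arm: 96.9%. If the excluded 13.5% gain nothing, the difference is 20 × 300/347 = 17.3 points and power is 89%.
- At 16.5 points: 85.9%. Diluted to 16.5 × 300/347 = 14.3 points: 72.4%.

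**The case against.** The strongest reply is that unequal dosing is not shown. One dose at any time satisfies the first criterion, subjects may enter up to 30 days into therapy (Section 3.2) and then qualify with their next dose, and Section 5 says that enrolment leaves treatment unaffected. The background material on navigation concerns completing treatment and starting it sooner, and a criterion without a time window ignores timing. If navigation did get more subjects dosed, the filter would work against ONN, so most of the two-sided rates above are false control wins. This stands, and it limits what can be said about size and direction. It does not make exclusions equal: Section 1.1.6 credits navigators with securing the resources patients need to complete treatment, and Section 5.1 lists expediting care as an aim.

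Other points stand in part:

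- Section 8.2 lets the investigator remove subjects, and the documents do not say whether every undosed subject stays on study. But being undosed is not itself listed as a reason for removal.
- Section 11.5.2 already reports disposition, and Section 11.5.5 plans adjusted models. The former gives no effect estimate; the latter addresses only measured factors, within the same selected set.
- The ACU ratios weight subjects equally. Weighted by person-time (assuming exponential survival, a 12-month cap and 20% undosed survival), 1.15 falls to about 1.06 and 1.07 to about 1.03.
- Making ITT primary now is debatable, because the interim looks and the re-estimation used the evaluable set.

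**Conclusion.** The concern holds and must be fixed. As written, every effect estimate for both co-primary endpoints comes from a post-randomisation subset, and the rule discards outcomes that are known. In the main scenarios the spurious OS6 difference is about 0.5 to 5 points. The top end needs a threefold difference in undosed share and only 20% six-month survival among the undosed. Bias could hide an effect or create one. All exclusion splits are assumptions, and under balanced, similarly selected exclusions there is no bias under the null. What is certain from the text is that the plan contains no randomisation-protected estimate with which to tell these cases apart.

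**What to change.** Amend Section 11.4, before anyone deciding on the amendment sees outcomes by arm, so that OS6, OS, OS12 and ACU are also analysed in all randomised subjects by assigned arm. The minimum, and the part that must be done, is a named, prespecified analysis reported beside the evaluable-set result; making it primary would be preferable. State who has seen arm-level data: Section 11.5.8 describes blinding for the efficacy looks but not for the futility look.

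- **OS6:** use every known 6-month status. Estimate by Kaplan-Meier at 6 months, censoring at last known alive those who leave early or have not yet reached 6 months, and compare arms as Section 11.5.5 does at 12 months. Add a tipping-point analysis for those who leave alive before 6 months.
- **ACU:** include all randomised subjects, with log observed time from randomisation to off-intervention as the Poisson offset. State that collection stops at off-intervention and that one exit criterion in Section 8.1 applies to one arm only: "Subjects randomized to the ONN arm withdraws consent to participate in the LPNP". Follow-up can therefore still differ by arm.
- **Reporting:** give exclusions by arm, criterion and vital status.

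The analysis trigger in Section 11.5.1 can stay.

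**Cost.** An SAP amendment with no extra enrolment. Withdrawals still rest on a censoring assumption, and removing the arm-dependent end of ACU follow-up would need a change to data collection that this amendment does not deliver. If ITT became primary, power could fall to about 72% in the least favourable case above, below the 80% target; the added analysis alone leaves the primary power unchanged.

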11.5 Analysis Methods

11.5.1 Timing of Analysis

An interim analysis will occur after 100 subjects have been enrolled in the evaluable population. A second interim analysis will occur after 85 deaths have occurred in the evaluable population. A third interim analysis will occur after 120 deaths have occurred in the evaluable population. Analyses of the primary objectives will occur after 300 subjects have been enrolled in the evaluable population. A final analysis will occur when the OS censoring rate reduces to 20% or when all surviving subjects (who remain on study) are on study for at least 30 months (whichever occurs first).

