11.3 Endpoints

11.3.1 Definition of Primary Endpoints

Overall survival at 6 months (OS6) will be determined as a binary variable indicating whether or not the subject was alive at 6 months following randomization.

Acute care utilization visits will be calculated for each subject as the total number of acute care visits normalized to an annual basis. Acute care visits will include unplanned hospital admissions, ED visits, and urgent care visits.

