11.5.8 Interim Analysis

After 100 subjects have been enrolled in the OS evaluable population, a formal interim analysis will be conducted. The interim analysis is designed primarily to assess futility regarding the 6-month OS rate objective and will be based on the conditional power. If the conditional power falls below 50%, the OS6 objective may be removed from the co-primary objective. If this occurs, the primary objective will be based only on the acute care utilization objective. With this revised design, 158 evaluable subjects would provide 90% power to detect a 20% reduction in acute care utilization from 6 visits per year in the non-navigation arm based on a 2-sided alpha = 0.05 significance level.

If the OS6 conditional power is greater than 50% but less than 80%, the sample size may be increased so that the power for the revised sample size is maintained at 80%. As discussed in Chen et al, 2004, this sample size re-estimation will not inflate the type I error.

Sample size re-estimation

As per protocol, the interim futility analysis occurred on 9/22/2022. Based on the results of the interim analysis and on the initial statistical design, the trial will proceed with OS6 and ACU as co-primary

endpoints. In order to retain 80% power for the OS6 objective, the sample size will be increased from 107 evaluable subjects per arm to 150 evaluable subjects per arm.

In order to achieve a total of 300 evaluable subjects, it is estimated that approximately a total of 347 subjects may be enrolled.

Additionally, ~~an~~ interim efficacy analysisanalyses will be performed after 85 and 120 deaths in the evaluable population have occurred (Interim Efficacy Analysis I and II). This will be conducted under the auspices of the LCI DSMC and will be blinded to the Sponsor-Investigator and the study conduct trial site. If, in the clinical judgement of the LCI DSMC, there are impelling favorable OS trends, the study may be terminated due to ethical considerations. No formal statistical stopping rules will be utilized, and no alpha spend will be incurred due to this interim efficacy evaluation.

As per protocol, Interim Efficacy Analysis I occurred on 1/23/2022. Based on the results of the blinded survival analysis and the updated statistical design (following the interim futility analysis on 9/22/2022), the trial will continue and Interim Efficacy Analysis II will be performed after 120 deaths in the evaluable population have occurred.

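### Early deaths join the evaluable population at once and survivors only at month 6, so a look cut before subjects mature modestly understates survival in both arms

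*Combined protocol and SAP*

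**What the plan says.** Section 11.4 sets two conditions for the evaluable population. The first is treatment: "Receive at least one dose of standard of care systemic anti-cancer therapy on or after the enrollment date". The second concerns outcome and time: "Die within six months of enrollment or otherwise are on study for at least 6 months". The same section applies this set throughout: "The evaluable population will be used for the analyses of all primary, secondary, and exploratory endpoints and interim analyses".

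Section 11.5.1 times the looks by counts within that population. For the futility look: "An interim analysis will occur after 100 subjects have been enrolled in the evaluable population". For Interim Efficacy Analysis II: "A third interim analysis will occur after 120 deaths have occurred in the evaluable population". For the primary analysis: "Analyses of the primary objectives will occur after 300 subjects have been enrolled in the evaluable population". An efficacy look at 85 deaths is also listed.

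Section 11.3.1 defines OS6 as a "binary variable indicating whether or not the subject was alive at 6 months following randomization", and Section 11.5.4 estimates it as a simple proportion per arm. Section 11.3.2 defines OS in the usual way, with living subjects censored when last known alive. No section limits a look to subjects randomised at least 6 months before the cutoff, closes the cohort in enrolment order, or waits for pending subjects to mature.

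**The concern.** Membership of the analysis set depends on the outcome. Of two dosed subjects randomised 2 months before a cut, the one who has died is in and the one who is alive is out. OS6 is a simple proportion, so censoring cannot repair this. The Kaplan-Meier curves do not repair it either, because the living recent subjects are absent from the risk set.

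Two uses of the data are affected. The first is the reported OS6 rates at the primary analysis. The second is the survival curves at Interim Efficacy Analysis II, where Section 11.5.8 lets the DSMC stop the trial on its clinical judgement of OS trends, with no formal boundary. A committee judging by eye should see standard curves. The 100-subject look used the same population for its conditional-power rule: "If the conditional power falls below 50%, the OS6 objective may be removed from the co-primary objective".

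**Working it through.** **Inputs from the plan.** Control median OS is 8 months, exponential (Section 11.2): 0.5^(6/8) = 59.5%, which reproduces the plan's approximate 60%. OS6 with navigation is 80% (Section 11.2). Planned enrolment of 347 for 300 evaluable (Sections 11.2 and 11.5.8) gives 300/347 = 86.5%. Accrual over 48 months (Sections 1.3 and 5) gives 347/48 = 7.23 per month.

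**Assumptions.** Accrual is uniform, non-evaluability is random, survival is exponential, and the data are cut when the trigger is reached.

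**Step 1: early deaths admitted ahead of their contemporaries.** Evaluable accrual per arm is λ = 7.23 × 0.865 / 2 = 3.127 per month. With 6-month survival p, the hazard is h = −ln(p)/6. Deaths by the cut among subjects randomised in the last 6 months are d = λ × [6 − (1 − p)/h].

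- Control, p = 0.60, h = 0.0851: d = 3.127 × (6 − 4.698) = 4.07.
- Navigation, p = 0.80, h = 0.0372: d = 3.127 × (6 − 5.378) = 1.95.

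The total is about 6.0 deaths. Living subjects left out number 2 × 6 × 3.127 − 6.0 = 31.5.

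**Step 2: the estimate.** Everyone in the set has a known 6-month status, so the 6-month Kaplan-Meier value equals the simple proportion p × m / (m + d). Here m is the number per arm randomised at least 6 months before the cut.

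**Step 3: the 120-death look.** Expected deaths per arm by month T are λ × [T − (1 − e^(−hT))/h]. At T = 34.4 this gives 72.8 + 46.9 = 119.7, so the look falls near month 34 of 48 with accrual open. Then m = 3.127 × 28.4 = 88.8.

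- Control: 0.60 × 88.8 / (88.8 + 4.07) = 57.4%.
- Navigation: 0.80 × 88.8 / (88.8 + 1.95) = 78.3%.

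Simulation of the same rule gives about 57.4% and 78.0%. Adding the living recent subjects with ordinary censoring gives about 60.0% and 79.7%. The gap is 20.6 points against 19.7.

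**Step 4: the 300-evaluable primary analysis.**

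- *Accrual still open.* m = (300 − 6.0)/2 = 147. Control is 0.60 × 147 / 151.07 = 58.4%, and navigation is 0.80 × 147 / 148.95 = 79.0% (78.8% simulated). The bias is about 1.6 and 1.2 points. This case needs (300 + 31.5)/0.865 = 383 enrolled.
- *Enrolment stopped at 347.* 347 × 0.865 = 300, so the 300th evaluable subject is close to the last to mature. Simulations with 86.5% to 90% evaluable give a bias of about 0.1 to 1.2 points per arm.
- *All subjects mature.* The bias is zero.

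**Step 5: the 100-evaluable look, if accrual was open.** m = (100 − 6.0)/2 = 47. Control is 0.60 × 47 / 51.07 = 55.2%, and navigation is 0.80 × 47 / 48.95 = 76.8%. Simulation with control at 59.5% gives 54.6% and 76.9%, a bias of −4.9 and −3.1 points. The gap is 22.3 points against a true 20.5.

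**Step 6: sensitivity and test validity.** With accrual open at 3.6 to 10.8 per month (an assumed range), the control/navigation bias runs from −0.9/−0.5 to −2.3/−1.6 points at 300 evaluable, and from −2.4/−1.7 to −7.1/−4.8 at 100. Weibull shapes of 0.8 and 1.3 change little. With equal arms, the two-sided 0.025 test rejects in about 2.5% of simulated trials at 300 and 2.1% to 2.4% at 100.

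**Step 7: the date rule.** Restricting the set to subjects randomised at least 6 months before the cut returns 59.5% and 80.0% at the 300 trigger (about 294 subjects), against true values of 59.5% and 80.0%.

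**The case against.** The strongest reply concerns size. The synopsis allows up to 347 subjects, and the open-accrual figure of 58.4% vs 78.8% needs about 383. Under the planned ceiling the primary bias is around 1 point at most. Section 11.5.1 also places the analysis after 300 are evaluable and does not say the data are frozen that day. Both arms follow the same rule and shift the same way, and the DSMC's question is about the difference between arms. All of this stands. It limits the point at the primary analysis to a small bias in the reported rates.

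It does not dispose of the 120-death look. There accrual is still open under the plan's own accrual period, and about 31 living subjects would be missing from the curves.

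A reader might infer more than the documents support:

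- *That the primary test is invalid or a difference is manufactured.* The inclusion rule is the same in both arms, and type I error stays at its nominal level.
- *That survival is understated in every sense.* The direction is relative to the mature evaluable population. Deaths before a first on-study dose are never evaluable, which pushes survival the other way.
- *That every OS analysis must move to all randomised subjects.* The final analysis waits for 20% censoring or 30 months on study, by when this mechanism has gone.
- *That the increase from 107 to 150 per arm was wrong.* The interim data and the handling of that cutoff are not given.

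**Conclusion.** The point holds as a modest bias in arm-level survival that follows from Sections 11.4 and 11.5.1. It matters most for what is still to come at Interim Efficacy Analysis II: about 2 to 3 points per arm, with the gap widened by about 1 point. At the primary analysis it is about 0.1 to 1.2 points per arm if enrolment stops at 347, about 1.2 to 1.6 if accrual runs past that, and zero if all subjects mature. The gap there moves by less than 1 point.

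The 100-evaluable look was exposed most, at about −5 and −3 points if accrual was open, with the gap widened by about 1.8 points (22.3 − 20.5). It has already taken place, so only the handling of its cutoff can be recorded.

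The sizes rest on uniform accrual, random non-evaluability, the plan's survival rates and a cut at the trigger. The direction rests only on the inclusion rule and a cut made while some subjects are immature. Nothing here shows that a change of this size would alter the DSMC's judgement. The case for acting is that the bias is avoidable at almost no cost.

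**What to change.** 1. **OS6.** Include only subjects who otherwise meet the evaluable criteria and were randomised at least 6 months before the data cutoff. Run the analysis when 300 such subjects qualify or when all enrolled subjects have matured, whichever comes first. The second limb is needed because, at 86.5% evaluable and a ceiling of 347, the count reached 300 in only about 54% of simulated trials.
2. **Interim Efficacy Analysis II.** Include all dosed subjects randomised by the cutoff, with survivors censored when last known alive as in Section 11.3.2. Drop the 6-months-on-study condition for this look.
3. **Looks already done.** Record how the cutoff was set and how living subjects under 6 months were handled, above all for the 100-evaluable look.

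The cost is SAP wording and possibly a slightly later primary cut. Treatment, visits and data collection do not change, and the final OS analysis needs no change for this reason. Living subjects who leave before month 6 are excluded while early deaths stay in. That is a separate issue which a date rule does not cure.
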